11.6 Urine Drug Screen

Urine samples are to be collected by the research assistant at the 13-week follow-up visit by use of collection cups with temperature-controlled monitoring strips. These cups will be provided by the manufacturer as noted in the Operations Manual, and will provide a rapid measure of the presence of the following: opioids, methadone, benzyolecognine (a cocaine metabolite), amphetamines, cannabinoids, and benzodiazepines.

11.7 Breath Alcohol Test

A breath alcohol test for measuring the presence of alcohol will be administered by the research assistant at the 13-week follow-up visit. The results will be recorded on the breath alcohol form, which is a common battery form for the CTN. The details of the manufacturer and the process for obtaining and recording results of this test will be defined in the Operations Manual.

11.8 TCG Participant Contact Form

The TCG participant contact form will capture the TELE counselor's attempts to contact a participant (randomized to the TCG only) and the actual successful contact information.

11.9 Week 13 Continuing Care Compliance Form

This form will document the extent of all participants' involvement, knowledge, and satisfaction in their prescribed continuing care plan.

11.10 Serious Adverse Events CRF

Serious adverse events, as defined in section 12.3.3.1, if reported to the TELE counselor during telephone contacts made at weeks 1, 2, 4, 6, 8, 10, and 12, or as elicited by the research assistant during the 13-week follow-up visit, will be addressed by the TELE counselor or the research assistant. Serious adverse events (which occurred from the time of randomization through the 13-week follow-up visit, and not previously recorded) which are reported to the TELE counselor during the scheduled telephone calls, or which are elicited by the research assistant during the 13-week visit, will be recorded on the SAE CRF and reported, as described in section 12.3.3.2.

Prior to study implementation, each site will have a documented plan describing their procedures in cases of suicidal or homicidal threats or attempts or other medical emergencies. During the course of the intervention period and at the follow-up visit, if participants are found to be in acute need of psychiatric attention for threats of these types or to have any condition requiring medical attention, the participant will be referred per the CTPs documented plan to community referral resources, including a medical care facility, readily available community hotlines, or other appropriate resources.

All SAEs determined to be related (refer to section 12.3.3.3) are to be brought to the attention of NIDA/CCTN medical monitor, the Lead Node medical monitor, and the local node/site PI within 24 hours of learning of the event and the local Institutional Review Board (IRB) per local requirements.

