10.4 Intervention after Discharge

Following discharge, a total of 7 telephone contacts at weeks 1, 2, 4, 6, 8, 10, and 12 will be made by the TELE counselor to all participants randomly assigned to the TCG. Each contact will follow the scripted procedure outlined in the Counselors Manual. The same procedure will be followed upon each contact. Up to 3 attempts will be made to contact the participant for each of the 7 scheduled calls, regardless of the outcome of the previously scheduled call.

Unless consent to participate is expressly revoked by the individual, he or she will continue to be contacted as scheduled. Attempts to contact the participant and the outcome of the call will be recorded on the participant contact form in the CRF. The SCG participants will not be contacted by the TELE counselor following their pre-discharge session.

A portion of calls will be recorded and at least 10% of successful calls will be randomly selected and scored for fidelity to the intended call procedures. Each node supervisor will provide supervision to the TELE counselor, per standard practice for the particular program.

In order to provide standardization across all TCG calls, the TELE Counselors Manual provides directions for conducting these calls. Information obtained during the course of the call will not be used as research data with the exception of serious adverse events. These events disclosed by the participant will be documented and reported as described in section 12.0.

The manual also provides minimal instructions for handling medical emergencies such as suicidal threats. Each facility is expected to have a written plan in place for emergency situations. If a plan is not in place, a procedure will be developed by the facility and should be available for review by the node quality assurance (QA) monitor prior to enrollment. Each facility has the responsibility for training its research staff on the facility's emergency plan.

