11.11 Study Completion Report

The Study Completion Report (SCR) is a brief tracking instrument used to officially record the time at which participants become inactive with respect to the study protocol. The SCR will be completed by the research assistant at the follow-up visit or the last planned contact, or upon early termination from the study, whichever occurs first.

11.12 Schedule of Instrument Administration:

Table 3 shows the timepoints at which each instrument is to be administered.

Table 3. Schedule of Instrument Administration

Instruments	Baseline	Randomization					Follow-up Visit (13–17 Weeks)			
			1	2	4	6	8	10	12	
Screening Form	X									
Randomization Form		X								
Locator Form	X	X								
HIV Risk Behavior Survey (RBS)	X									X
CTN ASI-Lite V1	X									
CTN ASI-Lite Follow-up V1										X
Urine drug screen										X
Breath alcohol test										X
TCG Participant Contact Form			X	X			X on	X ly)	X	
Week 13 Continuing Care Compliance Form										X
Serious adverse events CRF*										X
Study Completion Report (SCR)*										X
Verification Form*										X
* To be collected at termination of study participation.										

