12.3.2 Data and Safety Monitoring Board

12.3.2.1 Review of Data

The NIDA Clinical Trials Network Data and Safety Monitoring Board (DSMB), appointed by the NIDA CTN director, will conduct periodic reviews of safety and conduct of this trial. The DSMB will also review amendments to the study protocol. The DSMB will review data independently from the study sponsor, investigator(s), and IRBs to evaluate whether the accumulating data support continuing the trial for reasons relating to the randomization of study subjects and the safety of the study subjects. The DSMB will be provided with listings of SAEs to allow monitoring of patient safety, in summary tables of events or other formats preferred by the DSMB for their review. In conducting its reviews and making recommendations to NIDA regarding the status of this trial, the DSMB will assure that the safety of study subjects is protected while the scientific goals of the study are being met.

In addition, the DSMB will review the feasibility indicators of the trial to determine whether study procedures need to be changed to improve enrollment or whether attempts to accrue participants or access efficacy outcomes of the treatment under study are futile for the trial to continue. Since this is a feasibility trial, the DSMB will not base a

recommendation to terminate the trial early on either positive or negative efficacy trends, but instead on whether the efficacy data can be collected by the sites.

In order to assure the integrity of this study, DSMB members must agree to respect the confidentiality of the data they are asked to review. Members of DSMB will be asked to sign a statement of confidentiality confirming their agreement not to disclose data other than under the terms of this document.

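### SAEs can surface at up to 7 calls plus the visit in the call group but only at the visit in controls, so any arm-level reading could partly reflect detection (minor)

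*Protocol*

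**What the plan says.** **Routes.** Section 11.10 puts on the SAE CRF events "which are reported to the TELE counselor during the scheduled telephone calls, or which are elicited by the research assistant during the 13-week visit". It limits them to those "which occurred from the time of randomization through the 13-week follow-up visit, and not previously recorded".

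**Who is called.** Section 10.4 provides that "a total of 7 telephone contacts at weeks 1, 2, 4, 6, 8, 10, and 12 will be made by the TELE counselor", for TCG participants only. It adds: "The SCG participants will not be contacted by the TELE counselor following their pre-discharge session". The same section makes SAEs the one kind of call content that counts as data: "Information obtained during the course of the call will not be used as research data with the exception of serious adverse events".

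**Missed visit.** Section 10.6.3 has staff check continuing care attendance and, where the IRB allows, criminal justice activity. It does not mention SAEs.

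**CRF content.** Section 12.3.3.2 names a description, onset date, severity, relatedness and outcome. Where the event was learned is not among them.

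**Table 3 (Section 11.12).** The row "Serious adverse events CRF" has one mark, in the follow-up visit column, and its footnote reads "To be collected at termination of study participation". Section 12.3.3.3 requires a copy of the SAE CRF page with the 24-hour fax for a related SAE.

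**Use.** Section 12.3.2.1 states: "The DSMB will be provided with listings of SAEs to allow monitoring of patient safety, in summary tables of events". Section 13.4 plans end-of-trial listings and, unless the DSMB asks otherwise, blinded interim reports.

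**The concern.** The collection window is the same in both arms, but the scheduled chances for an event to come to light are not. A TCG participant who never attends week 13 may still have mentioned a hospitalization on a call. An SCG participant in the same position has no scheduled route. Among attenders, TCG also has earlier prompts that could catch events later forgotten.

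The data as described would not let an analyst separate the two sources. The rule that admits only unrecorded events means the week-13 record in TCG leaves out what the calls already found, and no source field is named that would allow it to be rebuilt. If SAEs were tabulated by arm for the DSMB or in a report, an excess in TCG could come from more listening rather than more events.

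Table 3 is a separate inconsistency. Read literally, it places the SAE form only at the end of participation, whereas Sections 11.10 and 12.3.3.3 need it whenever a call brings an SAE to light or a related SAE has to be faxed.

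**Working it through.** **Inputs from the Protocol**
- Calls: weeks 1, 2, 4, 6, 8, 10 and 12 (10.4). The count is 7, which matches the stated 7 and TELE calls 1–7 in Table 1.
- Counselor contacts in SCG after the pre-discharge session: 0 (10.4).
- Week-13 visit: 1 in each arm (10.6.1).
- Arm size: 180 (3.0).
- Missing at follow-up: 20% or fewer (13.3.1).

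**Step 1: scheduled occasions.** TCG 7 + 1 = 8; SCG 0 + 1 = 1. These are not eight equal assessments: 11.10 has events reported to the counselor but elicited by the research assistant.

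**Step 2: participants with no scheduled SAE route.** At the 20% ceiling, 0.20 × 180 = 36 in SCG. The same number in TCG would still have up to 7 calls each.

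**Step 3: expected ratio if true SAE rates are equal.** Let m be the share missing the visit, r the chance that the visit recovers an event in an attender, and c the chance that an event surfaces on a call. The documents give neither r nor c; both are assumed. Taking the three as independent of each other and of having an SAE:

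- SCG captured share = (1 − m) r
- TCG captured share = (1 − m)[1 − (1 − r)(1 − c)] + m c

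With m = 0.20:

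| r | c | SCG | TCG | Ratio |
|---|---|---|---|---|
| 1.0 | 0.25 | 0.80 | 0.80 + 0.05 = 0.85 | 1.06 |
| 1.0 | 1.00 | 0.80 | 0.80 + 0.20 = 1.00 | 1.25 |
| 0.8 | 0.25 | 0.64 | 0.80 × 0.85 + 0.05 = 0.73 | 1.14 |
| 0.8 | 0.50 | 0.64 | 0.80 × 0.90 + 0.10 = 0.82 | 1.28 |
| 0.8 | 1.00 | 0.64 | 0.80 × 1.00 + 0.20 = 1.00 | 1.56 |

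With m = 0.10 the ratio is 1.03–1.11 for r = 1 and 1.10–1.39 for r = 0.8. With m = 0 and r = 1 it is 1.00. Recall as low as 60% at m = 0.20 would give 1.27–2.08.

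**Step 4: in events.** For an assumed true rate of 10%, there are 18 true events per arm. With m = 0.20, r = 0.8 and c = 0.5, TCG shows 18 × 0.82 = 14.8 and SCG 18 × 0.64 = 11.5, a gap of about 3.

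**Step 5: the independence assumption.** If people who miss the visit also cannot be reached by phone, the term m c vanishes and the ratio becomes [1 − (1 − r)(1 − c)] / r. That is 1.00 for r = 1, and 0.85/0.8 = 1.06 to 1.00/0.8 = 1.25 for r = 0.8. In the other direction, the SAE definition in 12.3.3.1 includes death and hospitalization, which can themselves prevent attendance. The share of events lost in SCG could then exceed the overall missed-visit rate.

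**Step 6: Table 3 against the text.** A form collected only at termination cannot accompany a 24-hour fax about a related event disclosed on the week-2 call. The table and Sections 11.10 and 12.3.3.3 cannot all be followed literally.

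**The case against.** The strongest reply is that no planned comparison is harmed. Section 13.4 plans listings, does not name arm among their items, and blinds interim reports unless the DSMB asks otherwise. No SAE test or comparative safety objective is set, relatedness is judged event by event, and any by-arm table would normally be left to an SAP that is not shown. This stands, and it is why the point is minor.

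Second, a reader might infer that TCG will show more SAEs even with no true difference. The documents do not support that as a certainty. The visit looks back to randomization in both arms, so among attenders only recall differs, and hospitalizations and disabling events are comparatively memorable. Calls take SAEs passively and focus on adherence to the care plan. The size rests on r and c, which the documents do not give.

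Third, one might say that a control who misses the visit has no route at all. That is true only of scheduled, named routes. Participant-initiated contacts are logged in both arms (10.5), the research assistant may speak to participants when scheduling the visit (10.6.1), and 12.3.3.1 counts events observed by staff.

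Fourth, it is tempting to conclude from Table 3 that sites would hold back an SAE heard on a call. The footnote also covers the Study Completion Report and the Verification Form, so it may only mean when forms are gathered, and 11.10 and 12.3.3.3 are explicit. What stands is the inconsistency, not a predicted delay.

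Finally, admitting only unrecorded events is an ordinary way to avoid duplicates, the onset date is collected, and the contact form documents successful calls. But the onset date does not show where an event was first learned. The CRF itself is not shown, so it can only be said that the Protocol names no source field.

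**Conclusion.** The point holds as a limit on interpretation, and its severity is minor. Scheduled SAE ascertainment differs by arm, and the Protocol names nothing that would let an analyst separate detection from occurrence. It does not invalidate a planned analysis, because none compares SAEs between arms.

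The direction, if there is a bias, is towards more recorded SAEs in TCG. Its size is unknown. At the Protocol's 20% ceiling for missing follow-up, the expected ratio is about 1.06 to 1.56, resting on assumed visit recall of 80–100%, assumed call capture of 25–100%, equal attendance in both arms and independence. It falls to 1.00 with full attendance and perfect recall, and to 1.00–1.25 if those who miss the visit are also unreachable by phone. Table 3 and its footnote do not agree with Sections 11.10 and 12.3.3.3 and need reconciling.

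**What to change.** - In 11.10, have the research assistant ask both arms the same week-13 question about all SAEs since randomization, whether or not already recorded.
- Add one field to the SAE CRF for where the event was first learned (call, week-13 visit, other contact).
- In 13.4, state that if SAEs are summarised by arm, the summary uses week-13-elicited events, shows visit attendance by arm alongside, and lists call-reported events separately. Attendance is needed because week-13 counts still miss every non-attender; the change reduces the difference in ascertainment but does not guarantee comparability.
- Reconcile Table 3 and its footnote with 11.10 and 12.3.3.3.

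Cost: one CRF field, short additions to two sections and a correction to one table, with no new contacts or staff. The downside is that some TCG events will be reported from two sources and must be matched so that each is counted once.

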11.11 Study Completion Report

The Study Completion Report (SCR) is a brief tracking instrument used to officially record the time at which participants become inactive with respect to the study protocol. The SCR will be completed by the research assistant at the follow-up visit or the last planned contact, or upon early termination from the study, whichever occurs first.

11.12 Schedule of Instrument Administration:

Table 3 shows the timepoints at which each instrument is to be administered.

Table 3. Schedule of Instrument Administration

Instruments	Baseline	Randomization					Follow-up Visit (13–17 Weeks)			
			1	2	4	6	8	10	12	
Screening Form	X									
Randomization Form		X								
Locator Form	X	X								
HIV Risk Behavior Survey (RBS)	X									X
CTN ASI-Lite V1	X									
CTN ASI-Lite Follow-up V1										X
Urine drug screen										X
Breath alcohol test										X
TCG Participant Contact Form			X	X			X on	X ly)	X	
Week 13 Continuing Care Compliance Form										X
Serious adverse events CRF*										X
Study Completion Report (SCR)*										X
Verification Form*										X
* To be collected at termination of study participation.										

12.0 REGULATORY AND REPORTING REQUIREMENTS

12.1 Institutional Review Board Approval

Prior to initiating the study, the investigator at each study site will obtain written Institutional Review Board (IRB) approval for the protocol and the participant informed consent form. Should changes to the study protocol become necessary after initial IRB approval is obtained, protocol amendments will be prepared by the Lead Node and must be submitted in writing to each participating Node's IRB by the investigator for his or her CTP. Written IRB approval is necessary prior to implementation of the protocol. In addition, IRBs will approve all advertising materials used for participant recruitment and any educational materials planned to be provided to the participant.

12.2 Informed Consent

All candidates for the study will be given a copy of the informed consent form approved by their IRB to read. The consent form may be read to any participant who is unable to read. The research assistant at each site will explain all aspects of the study in lay language and answer all of the candidate's questions regarding the study.

Any individual who wants to participate in the study will be asked to sign the informed consent. A copy of the signed consent form will be made and given to the participant. No information for the study will be obtained, or any study procedure performed, prior to the informed consent being signed by the participant.

Individuals who refuse to participate in the study or who withdraw from the study after providing consent will be treated without prejudice or penalty. The reason for refusal or withdrawal will be noted in the screening/enrollment log.

Because of the potential time lapse between actually obtaining written consent and randomization, the research assistant will remind each participant just prior to randomization of the voluntary nature of study participation and the right to withdraw consent to participate at any time.

12.3 Data and Safety Monitoring Plan

12.3.1 Clinical Monitoring

Prior to site enrollment, the Lead Node and node QA monitor is responsible for assuring that proper study-related documentation exists. The Lead Node QA monitor also assists in training investigators and other site personnel in study procedures and good research practices. Additionally, the Lead Node QA monitor will conduct a site initiation visit. The TELE Protocol Initiation Endorsement Form will be signed by the node PI, the lead investigator, and the NIDA representative to authorize site enrollment.

All investigators will allow representatives of their local node, Lead Node, and NIDA or its representatives to periodically visit the participating CTP at mutually convenient times during and after the study. The purpose of these visits will be to assure that submitted data are accurate and in agreement with source documentation, and that all essential documentation required by good research practice guidelines is appropriately filed. In order to complete the required monitoring, these periodic monitoring visits will occur more frequently at the beginning of the study and as needed for the remaining duration.

In order to provide adequate monitoring for this feasibility trial of limited duration for subject participation (3 months) and minimal risk to participants, the following are the minimum requirements to be performed by the node QA monitor at each site:

- All informed consent documents will be reviewed to verify that consent for study participation has been properly obtained and documented prior to performance of any study specific procedures.
- All reportable serious adverse events (as defined in section 12.3.3.3) will be reviewed.
- All source data verification will be performed on a minimum of 5% of randomized participants.

Additionally, these monitoring visits provide the local node with the opportunity to evaluate the progress of the study at each of their sites and to inform the Lead Node or/and NIDA of potential problems at the study sites. Prior to leaving the site, the node monitor will conduct an exit meeting with the site investigator and/or study personnel to review and clarify preliminary findings, which include any outstanding items and the appropriate plan of action. These activities and findings will be documented in a visit report by the node QA monitor and will be distributed to the site investigator, node PI, Lead Node PI, and NIDA.

Throughout the trial, the Node QA Monitor or designee will maintain phone contact with participating sites to address study progress.

At the end of the study, the node QA monitor will perform close-out activities necessary to conduct a final review of the study administrative and regulatory records, to ensure that all outstanding issues are resolved, and to review record maintenance and archival requirements with the site.

12.3.2 Data and Safety Monitoring Board

12.3.2.1 Review of Data

The NIDA Clinical Trials Network Data and Safety Monitoring Board (DSMB), appointed by the NIDA CTN director, will conduct periodic reviews of safety and conduct of this trial. The DSMB will also review amendments to the study protocol. The DSMB will review data independently from the study sponsor, investigator(s), and IRBs to evaluate whether the accumulating data support continuing the trial for reasons relating to the randomization of study subjects and the safety of the study subjects. The DSMB will be provided with listings of SAEs to allow monitoring of patient safety, in summary tables of events or other formats preferred by the DSMB for their review. In conducting its reviews and making recommendations to NIDA regarding the status of this trial, the DSMB will assure that the safety of study subjects is protected while the scientific goals of the study are being met.

In addition, the DSMB will review the feasibility indicators of the trial to determine whether study procedures need to be changed to improve enrollment or whether attempts to accrue participants or access efficacy outcomes of the treatment under study are futile for the trial to continue. Since this is a feasibility trial, the DSMB will not base a

recommendation to terminate the trial early on either positive or negative efficacy trends, but instead on whether the efficacy data can be collected by the sites.

In order to assure the integrity of this study, DSMB members must agree to respect the confidentiality of the data they are asked to review. Members of DSMB will be asked to sign a statement of confidentiality confirming their agreement not to disclose data other than under the terms of this document.

